5.3 Treatment assignment and randomization

Subjects were randomized and stratified based on gender into two groups using block randomization based on a schedule provided by the study statistician, [name], Indiana University School of Medicine Department of Biostatistics.

The randomization code was provided to Amgen as part of the ISS contract agreement.

5.4 Treatment blinding

Subjects, investigators and study staff will remain blind to the identity of the treatment from the time of randomization until database lock. The randomization code will be kept strictly confidential and the identity of the study drug treatments will be concealed using identical packaging and labeling. The blind will only be broken in an emergency where it is essential to know which treatment a subject received in order to give the appropriate medical care.

5.5 Dispensing of study drug

The investigational products (EREN and EREN-P) supplied in prefilled syringes will be shipped by Amgen to the attention of the unblinded IU Health Investigational Drug Services Pharmacy. The IU Health Pharmacy will dispense the investigational products according to a randomization schedule provided by the study statistician, [name]. A written prescription order form will be completed by the licensed study dentist and submitted to the pharmacy each time study drug is requested for a subject. Doses will be administered in the upper arm, thigh, or abdomen by a study dentist qualified in s.c. drug administration.

Study product will be stored and handled according to labeling instructions: store refrigerated at 2°C to 8°C (36°F to 46°F) in the original carton to protect from light until time of use; do not freeze; and do not shake; leave the prefilled syringe at room temperature for at least 30 minutes before injecting. The investigational products will be stored in a secured area of the IU Health Investigation Drug Services Pharmacy to which only the pharmacy staff have access.

The IU Health pharmacy will maintain adequate records documenting the receipt, use, loss, or other disposition of the products on the electronic Investigational Agent Accountability Record. The log will identify the products and account for the disposition including specific dates and

quantities used/dispensed and returned, as applicable. The log will capture the electronic signatures of the site designees who dispensed and verified the products.

The clinical site, OHRI, working with the pharmacy will also maintain a Drug Administration Form documenting the date and time of transport to the blinded site staff, the date and signature of the blinded site staff receiving the study drug, the date and time the study drug was received from the pharmacy, the date and time the study drug was administered, and the injection site body location.

6. Visit Schedule and Assessments

Study Schedule

| Period | Screening | Treatment Period | | | | | | Post-Treatment |
|---|-----------|------------------|------|------|-------|-------|-------|----------------|
| Visit Name | Screening | Baseline | Wk 4 | Wk 8 | Wk 12 | Wk 16 | Wk 20 | Wk 24 |
| Days | -28 to -1 | 1 | 29 | 57 | 85 | 113 | 141 | 169 |
| Weeks | -4 to -1 | 0 | 4 | 8 | 12 | 16 | 20 | 24 |
| Informed consent | X | | | | | | | |
| Randomization | | X | | | | | | |
| Study drug administration | | X | X | X | X | X | | |
| Inclusion / Exclusion criteria | X | | | | | | | |
| Demography | X | | | | | | | |
| Medical history/current medical conditions | X | | | | | | | |
| Prior therapy for TMD | X | | | | | | | |
| Adverse Events | X | X | X | X | X | X | X | X |
| Concomitant medications | X | X | X | X | X | X | X | X |
| Familiarize with PEG App | X | X | | | | | | |
| BPI, PEG and pain medication assessment (daily), JFLS-8, PHQ-4, SSS-8 | | X | X | X | X | X | X | X |
| PGIC | | | X | X | X | X | X | X |

Screening Visit: Subjects will complete the informed consent process, being given ample time to review the consent and to ask any questions they have before deciding if they wish to participate. Those interested will sign and date their informed consent and the consent will also

be signed and dated by the person reviewing the consent process with them. Subjects will receive a signed copy of their consent before leaving this visit. A Study Dentist qualified to diagnosis TMD will review the potential subject's health history, medications and TMD history for the inclusion and exclusion criteria.

The Diagnostic Criteria for Temporomandibular Disorders Symptom Questionnaire (Appendix C) and DC/TMD Examination Form (Ohrbach, 2016) will be used to confirm the TMD diagnosis and determine whether subjects meet the inclusion/exclusion criteria. To meet the diagnostic criteria for TMD Myalgia (ICD-9 729; ICD-10 M79.1) (Schiffman et al., 2014), subjects must have a history of pain of muscle origin that is affected by jaw movement, function, or parafunction, and demonstrate replication of this pain with provocation testing of the masticatory muscles. The specific criteria (Schiffman et al., 2014) include having a positive history for both pain in the jaw, temple, in the ear, or in front of ear and pain modified with jaw movement, function or parafunction. During clinical examination, subjects must have a confirmation of pain in the temporalis or masseter muscle(s) and report familiar pain in the temporalis or masseter muscle(s) with at least one of the following provocation tests: palpation of the temporalis or masseter muscle(s) or maximum unassisted or assisted opening movement(s).

Subjects with smartphones will be asked to download the MyCap app and will then be trained on completing the PEG Scale and the pain medication assessment questions using their smartphone. The subject will be scheduled to return to the study site for their Baseline visit.

Baseline, Wk 4, 8, 12, and 16 Visits: The subject's medical history, medications and continuance criteria will be reviewed to assure the subject still qualifies to participate in the study. The Diagnostic Criteria for Temporomandibular Disorders Symptom Questionnaire (Appendix C) and DC/TMD Examination Form will be used to confirm the TMD diagnosis and determine whether subjects meet the inclusion/exclusion criteria. In addition, the subjects will be assessed using the Brief Pain Inventory (BPI) (Appendix D), PEG (Pain, Enjoyment, General Activity) Scale and pain medication assessment (Appendix E), Jaw Function Limitation Scale (JFLS) (Appendix G), Patient Health Questionnaire (PHQ-4) (Appendix H), and Somatic Symptom Scale (SSS-8) (Appendix I). Starting at week 4 the subjects will also be assessed using global improvement in pain as measured by the Patient Global Impression of Change (PGIC) (Appendix F).

The subject will receive their assigned treatment (EREN or EREN-P) based on the randomization scheme at baseline and Wk 4, 8, 12, and 16.

The procedure for texting each day will be reviewed with the subject and a practice text will be sent to assure communication is accurate. Subjects without smartphones will only be required complete the PEG Scale and pain medication assessment questions using the app onsite at Baseline and at all subsequent study visits.

Adverse events will be assessed and documented, and the subjects will be schedule for their next visit.

Wk 20 End of Treatment Period Visit: Subjects will be assessed using the BPI, PEG and pain medication assessment (app), PGIC, JFLS, PHQ-4, and SSS-8. Adverse events will be assessed and documented, and the subjects will be schedule for their next visit.

Wk 24 Post-Treatment Follow-up Visit: Subjects will return for follow-up examination and assessed using the BPI, PEG and pain medication assessment (app), PGIC, JFLS, PHQ-4, and SSS-8. Adverse events will be assessed and documented.

7. Safety Monitoring

This study will be conducted in compliance with the US Code of Federal Regulations (CRF) governing informed consent (21 CFR 50), Institutional Review Board (IRB) (21 CFR 56), and with applicable regulations governing Investigator conduct (21 CFR 312).

This study will be performed according to GCPs. SOPs for all procedures are on file with the Quality Assurance staff of the Oral Health Research Institute.

All study staff who have direct subject contact will be required to review the WARNINGS AND PRECAUTIONS for Hypersensitivity Reactions, Constipation with Serious Complications and Hypertension found in Section 5 of the US Prescribing Information (USPI) for Aimovig®.

https://www.pi.amgen.com/~/media/amgen/repositorysites/pi-amgen-com/aimovig/aimovig_pi_hcp_english.ashx

7.1 Adverse Events

Subjects will be questioned regarding any general health or oral complaints and symptoms they have experienced during each visit. Any findings will be documented on the AE CRF. In the event of subjects reporting AEs outside the scheduled clinical visit, the Investigator will assess them at the earliest opportunity.

All AEs, regardless of severity or relationship to the treatments, will be recorded. Serious AEs include any events resulting in death, decreased life expectancy, life-threatening situations, persistent or permanent disability/incapacity, hospitalization, or congenital anomaly/birth defect. In addition, other important medical events that are deemed clinically important/serious based on PI judgement will be recorded as AEs. Within 24 hours, the Investigator will submit a written report to Amgen documenting the circumstances of the serious AE.

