2.2 Secondary Objective and Outcome Measures

To assess the effects of Aimovig® (EREN) compared to placebo (EREN-P) based on the change in mean between-group difference in secondary outcomes during the 20-week trial and after 24 weeks (two months after the last treatment). The outcome measures are based on consensus recommendations for research assessments in chronic pain and TMD research (Ohrbach et al., 2016; Kroenke et al., 2019). *We postulated that Aimovig® will be superior to placebo in improving several secondary outcomes including:*

- a) Pain interference as measured by the BPI interference scale
- b) Trajectory of pain improvement based on changes in daily reporting of pain using the PEG (Pain, Enjoyment, General Activity) Scale as measured using an app downloaded on the subject's smartphone or for individuals without smartphones at baseline and every 4 weeks over the 24-week study period
- c) Days of use of TMD pain-specific medication per month
- d) Global improvement in pain as measured by the Patient Global Impression of Change (PGIC)
- e) Jaw function as measured by the Jaw Function Limitation Scale (JFLS-8)
- f) Depressive and anxiety symptoms as measured by the Patient Health Questionnaire (PHQ-4)
- g) Somatic symptom severity as measured by the Somatic Symptoms Scale (SSS-8)
- h) Safety and tolerance as measured by incidence of AEs and SAEs

3. Study Design

This was a 24-week, randomized, double-blinded, placebo-controlled, parallel group proof-of-concept study with two arms (active and placebo). The plan was to enroll 30 subjects. There was a four-week screening period to identify subjects that meet the diagnostic criteria (DC/TMD) for "myalgia", recommended by the International RDC/TMD Consortium Network and Orofacial Pain Special Interest Group (Schiffman et al., 2014). The Diagnostic Criteria for Temporomandibular Disorders Symptom Questionnaire and DC/TMD Examination Form (Ohrbach, 2016) was used during Screening and Baseline visits to confirm the TMD diagnosis and determine whether subjects met the inclusion/exclusion criteria.

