7.2 Serious Adverse Events

Safety monitoring for this study will focus on adverse events related to treatment use and unanticipated problems involving risks to participants, including unanticipated problems that meet the definition of a serious adverse event. At each visit, subjects will be queried about any adverse events that may have occurred since their last visit, regardless of direct relationship to treatment use. Adverse events will be recorded on an Adverse Event form. Abnormalities, or worsening of pre-existing conditions, observed by the examiner or reported by the subject that occur at any visit will be recorded on the AE CRF. All AEs will be transcribed onto a log, which will be monitored by the PI to determine if the nature, frequency, or severity of an event meets the criteria for prompt reporting. All adverse events will be reported to the IRB during annual review.

The PI will be notified immediately if a serious adverse event occurs. All serious adverse events that meet the prompt reporting requirements will be reported to the IRB within 5 business days. Serious adverse events include: any event resulting in death, is life-threatening, requires hospitalization, results in disability/permanent damage, congenital anomaly/birth defect, or requires intervention to prevent permanent impairment or damage, and/or other medical events.

The study site will be responsible for reporting SAEs to Amgen in accordance with the Amgen ISS Program contract requirements.

The study site will be responsible for reporting all safety information to Amgen in accordance with their reporting requirements ([Table 1](#)).

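### Section 7.1 records investigator-judged serious events as AEs while Section 7.2 can count them as SAEs, so they can fall outside the 24-hour supplier report and the SAE count

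*Combined protocol and SAP*

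**What the plan says.** The protocol defines serious events twice.

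- **Section 7.1, the list:** "Serious AEs include any events resulting in death, decreased life expectancy, life-threatening situations, persistent or permanent disability/incapacity, hospitalization, or congenital anomaly/birth defect".
- **Section 7.1, the next sentence:** "other important medical events that are deemed clinically important/serious based on PI judgement will be recorded as AEs".
- **Section 7.1, supplier report:** "Within 24 hours, the Investigator will submit a written report to Amgen documenting the circumstances of the serious AE".
- **Section 7.2, the list:** it repeats death, life-threatening events, hospitalization, disability and congenital anomaly, and closes with an event that "requires intervention to prevent permanent impairment or damage, and/or other medical events".
- **Section 7.2, IRB route:** "All serious adverse events that meet the prompt reporting requirements will be reported to the IRB within 5 business days". For events in general, "All adverse events will be reported to the IRB during annual review". All AEs also go onto a log that is "monitored by the PI to determine if the nature, frequency, or severity of an event meets the criteria for prompt reporting".

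Section 2.2 makes the classification part of a secondary outcome, item (h): "Safety and tolerance as measured by incidence of AEs and SAEs". Neither safety section refers to the other's list, and neither is named as the definition for outcome (h).

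**The concern.** Every event is recorded whichever section is read, so the conflict may look clerical. But the label has consequences. Section 7.1 ties the 24-hour report to the event being a serious AE, and outcome (h) reports SAEs as well as AEs. If the site follows 7.1 as written, an event the PI considers serious is entered as an AE. If it follows 7.2, the same event can be an SAE.

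The disputed category is not remote. Section 7 requires staff to review the product warnings on hypersensitivity, serious constipation and hypertension. Section 1 reports that one of five patients treated off-label stopped because of raised blood pressure. As a hypothetical illustration, an event of this kind that was managed without hospital admission, and that the PI nevertheless judged serious, could meet no other criterion in the 7.1 list.

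**Working it through.** No arithmetic applies. The check sets the two lists side by side and then follows the label to each place where it has an effect.

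**Step 1: compare the lists.**

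| Type of event | Section 7.1 | Section 7.2 |
|---|---|---|
| Death, life-threatening, hospitalization, disability, congenital anomaly | SAE | SAE |
| Important event judged serious by the PI | Assigned to AEs | Not named, but within the open closing category of SAEs |
| Needs intervention to avert lasting impairment | Not named | SAE |
| Decreased life expectancy | SAE | Not named, but could come under the open closing category |

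The second row is the positive conflict: 7.1 assigns the category to AEs, and 7.2's wording is wide enough to make it an SAE. The last two rows are differences in what is named. Both lists are introduced by a form of the verb include, so a criterion missing from one of them is not thereby excluded.

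**Step 2: follow the label.**

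- *Supplier report.* Section 7.1 requires the 24-hour report for a serious AE. An event entered only as an AE can fall outside it. Section 7.2 adds that SAE reporting follows the supplier's contract and that all safety information follows Table 1. Among individual reports, Table 1 as shown has rows for SUSARs and for pregnancy or lactation exposure but no general SAE row. Its footnote leaves specific requirements to the Research Agreement, which is not shown.
- *IRB report.* The SAE label alone does not trigger the 5-business-day report, because only SAEs meeting the prompt-reporting requirements are sent. The PI also screens every AE on the log for prompt reporting, whatever its label. The label therefore matters less on this route.
- *Outcome (h).* The event enters AE incidence either way. Whether it enters SAE incidence depends on the section applied.

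**Step 3: check whether another section settles it.** Section 8 lists the outcomes for the repeated-measures analysis. AEs and SAEs are not among them, and no definition is given there.

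**The case against.** The strongest reply is that AEs in 7.1 is a slip for SAEs. The sentence begins as an addition to the SAE list, describes events judged serious, and is followed at once by the 24-hour rule for serious AEs. Recording something as an AE also does not say that it is not an SAE, since every SAE is an AE. This is plausible, and it may well be what the authors meant. It does not remove the point: the sentence is an operative safety instruction, staff will follow it as printed, and correcting that one word would still leave two lists that name different criteria.

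A second reply is that 7.2 does not mention PI judgement or important events at all. That is right. It reaches them only through a closing phrase that has no limit. This is a weakness of 7.2 in its own right, and it means that simply aligning 7.1 with 7.2 would import an unbounded definition.

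A reader might go further and infer that under 7.1 these events would get no expedited report to anyone. The documents do not support that. The PI who judged the event serious also screens the AE log for prompt IRB reporting, and the supplier contract may impose its own rule. Section 7 also commits the study to GCP, to the federal investigator regulations and to SOPs on file.

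**Conclusion.** The two sections conflict on how to classify events that the PI judges serious, and two further criteria are each named in only one list. Followed as written, 7.1 can take such an event out of the 24-hour supplier report and out of the SAE part of outcome (h). The IRB route is partly protected by the log review. No comparable screen is stated for the supplier report.

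The size cannot be put as a number. The documents give no expected count of such events and no denominator for SAE incidence. No planned test changes, because Section 8 specifies none for AEs or SAEs, and the primary endpoint is untouched.

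The conclusion assumes that site staff apply the text as printed. Whether any report would actually be missed depends on the contract and SOPs, which are not shown. It would be wrong to infer from the text alone that reports were missed.

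**What to change.** Reconcile Sections 7.1 and 7.2 into one SAE list, and have both sections cite it.

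1. In 7.1, correct the sentence that records these events as AEs. Suitable wording: *any other important medical event that the PI judges to be serious is recorded and reported as an SAE.*
2. In 7.2, replace the unlimited closing category with the same bounded wording.
3. Carry the intervention criterion and the decreased-life-expectancy criterion into the common list.
4. State that the 24-hour supplier report, the IRB report and outcome (h) all use this list, and check it against the supplier contract.

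Parts of the document are written in the past tense. If conduct is complete, check the AE log against the common list before reporting outcome (h), and state which definition was applied during the trial.

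The cost is a wording change in two sections and possibly a few more expedited reports. If the trial is finished, it is one pass through the AE log of a study planned for 30 subjects.

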7.2 Serious Adverse Events

Safety monitoring for this study will focus on adverse events related to treatment use and unanticipated problems involving risks to participants, including unanticipated problems that meet the definition of a serious adverse event. At each visit, subjects will be queried about any adverse events that may have occurred since their last visit, regardless of direct relationship to treatment use. Adverse events will be recorded on an Adverse Event form. Abnormalities, or worsening of pre-existing conditions, observed by the examiner or reported by the subject that occur at any visit will be recorded on the AE CRF. All AEs will be transcribed onto a log, which will be monitored by the PI to determine if the nature, frequency, or severity of an event meets the criteria for prompt reporting. All adverse events will be reported to the IRB during annual review.

The PI will be notified immediately if a serious adverse event occurs. All serious adverse events that meet the prompt reporting requirements will be reported to the IRB within 5 business days. Serious adverse events include: any event resulting in death, is life-threatening, requires hospitalization, results in disability/permanent damage, congenital anomaly/birth defect, or requires intervention to prevent permanent impairment or damage, and/or other medical events.

The study site will be responsible for reporting SAEs to Amgen in accordance with the Amgen ISS Program contract requirements.

The study site will be responsible for reporting all safety information to Amgen in accordance with their reporting requirements ([Table 1](#)).

7.3 Study Withdrawal/Discontinuation

Subjects may withdrawal or discontinue from the clinical trial at any time without penalty or loss. Subjects will be advised at the start of the trial that they may withdraw from the trial at any time, without giving a reason. Subjects may be withdrawn by the Principal Investigator for the following reasons:

- the volunteer wishes to withdraw;
- if, in the opinion of the Investigator, it is in the best interests of the subject;
- if serious adverse reactions occur;
- inter-current illness occurs;
- there is a significant violation of the prohibitions and restrictions;
- development of an exclusion criterion.

Withdrawals due to non-attendance must be followed up to attempt to obtain the reason that the subject is 'lost to follow up'. Subjects who are lost to follow up will be encouraged to return to the site for an exit visit. Subjects withdrawn for medical reasons will be referred to a physician /dentist. Their condition will be monitored until it is resolved or clinically non-significant. All withdrawals and the reason for withdrawal will be documented. Withdrawn subjects will not be replaced.

8. Data Analysis

Mixed model repeated measures (MMRM) analysis will be used to evaluate changes over time in the BPI pain severity/intensity scale and BPI total score, PEG Scale total score and daily pain, days of use of pain medication and TMD pain-specific medication per month, JFLS-8, PHQ-4 anxiety and depression, SSS-8 Scale, and PGIC pain change within and between treatment groups. The MMRM will include factors for treatment group, time, and their interaction. Time will be repeated within subject. The MMRM will also include gender as a covariate due to stratification by gender in the randomization. The distribution of the outcomes will be examined and a transformation of the data will be used if necessary. A two-sided 5% significance level will be used for all tests without multiplicity adjustment between multiple endpoints.

